## 6.2 Randomization

Participants will enroll in the study at the first biopsy collection. Only participants who remain in the trial after the completion of the first biopsy visit will be randomized.

Accrual will continue until 24 participants have received first product administration.

The randomization sequence will be obtained by computer-generated random numbers and provided to each HVTN CRS through the SDMC via a Web-based randomization system.

Groups 1 and 2 will be randomized simultaneously.

The randomization will be stratified by assigned sex at birth and done in blocks to ensure balance across both groups.

## 6.3 Blinding

Participants and site staff will be unblinded as to participant treatment group assignments. VRC07-523LS concentration and ADA assessments will be performed in a blinded fashion.

## **6.4 Statistical analyses**

This section describes the final study analyses, unblinded as to treatment arm assignment.

All analyses pertaining to safety and drug levels objectives of the study will be conducted with an intent-to-treat analysis that includes all randomized individuals per their randomization allocation. Additional analyses will be performed that account for the actual infusions and dose levels that each participant received.

Analyses will be performed using SAS and R. Other software may be used to perform additional exploratory analyses. Unless otherwise stated, all tests will be two-sided and performed at a 5% significant level. In particular, no formal multiple comparison adjustments will be employed for multiple safety endpoints.

### **6.4.1 Analysis variables**

The analysis variables consist of baseline participant characteristics, safety, VRC07-523LS concentrations, and laboratory measurements for primary, secondary, and exploratory objective analyses.

### **6.4.2 Baseline comparability**

Treatment arms will be compared for baseline participant characteristics using descriptive statistics.

### **6.4.3 Safety/tolerability analysis**

All participants who received at least 1 partial or complete administration of VRC07-523LS will provide some safety data.

#### **6.4.3.1 Solicited AEs**

The number and percentage of participants experiencing solicited AEs, either signs or symptoms, will be tabulated by severity and treatment arm and the percentages displayed graphically by arm. For a given sign or symptom, each participant's solicited AEs will be counted once under the maximum severity for all administration visits. In addition to the individual types of events, the maximum severity of local pain or tenderness, induration or erythema, and of systemic symptoms will be calculated.

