**(A) VRC07-523LS (20 mg/kg IV)**

**(B) VRC07-523LS (10 mg/kg IV)**

**Figure 4-6 (A) VRC07-523LS was administered to male (n = 3) and female (n = 3) rhesus macaques at a dose of 20 mg/kg IV in a SHIV challenge study. (B) VRC07-523LS PK was measured in male (n = 2) and female (n = 2) cynomolgus macaques following a single administration of 10 mg/kg IV. Plasma concentrations were monitored by ELISA in both studies.**

Repeated administration of VRC07-523LS will permit further understanding of the mucosal antibody levels, their accumulation after repeated dosing, and the consequences of any antidrug responses, if they were to develop.

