#### 4.8 Potential risks of study products and administration

There is limited human experience with administration of VRC07-523LS. VRC 605 was already evaluating VRC07-523LS prior to the start of HVTN 127/HPTN 087 and thus far there have been no SAEs or Grade 3 or higher related AEs in HVTN 127/HPTN 087. In addition, the similar CD4-binding site mAb VRC01 has been given to more than 3000 adults and 60 infants in several phase 1 and phase 2b clinical trials. More than 10,000 infusions of 10 mg/kg and 30 mg/kg VRC01 have been given to HIV-uninfected adults in HVTN 703/HPTN 081 [NCT02568215] and HVTN 704/HPTN 085 [NCT02716675]. Both VRC01 and VRC01LS are being tested in an ongoing phase 1 study (HVTN 116).

Standard infusion reactions to mAb administration are typically mild but may include fever, flushing, chills, rigors, nausea, vomiting, pain, headache, dizziness, shortness of breath, hypertension, pruritus, rash, urticaria, diarrhea, tachycardia or chest pain (50). Most infusion reactions appear to result from antibody-antigen interactions resulting in cytokine release (50). Administration of mAbs may have a risk of severe reactions, such as acute anaphylaxis, serum sickness, angioedema, bronchospasm, hypotension, and hypoxia, the generation of ADAs; they may also be associated with an increased risk of infections. However, these reactions are rare and more often associated with mAbs targeted to human proteins (50) or with the use of murine mAbs, which have a risk of eliciting human anti-mouse antibodies (51). Infusion of mAbs directed against cell surface targets on lymphocytes may cause a reaction known as “cytokine release syndrome”, with clinical manifestations including fatigue, headache, urticaria, pruritus, bronchospasm, dyspnea, sensation of tongue or throat swelling, rhinitis, nausea, vomiting, flushing, fever, chills, hypotension, tachycardia, and asthenia (52). Cases of cytokine release syndrome occur most often in the first few hours after the first mAb dose, because the cytokine release is associated with lysis of the cells targeted by the mAb and the burden of target cells is greatest at the time of the first mAb treatment (52).

Since VRC07-523LS targets a viral antigen rather than human cell surface antigens and is a human mAb, severe infusion reactions are expected to be rare.

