## 5 Objectives and endpoints

### 5.1 Primary objectives and endpoints

*Primary objectives 1:*

- To evaluate the safety and tolerability of VRC07-523LS administered at 10 mg/kg IV infusion every 4 months
- To evaluate the safety and tolerability of VRC07-523LS administered at 30 mg/kg IV infusion every 4 months

*Primary endpoint 1:*

- Local and systemic Solicited AE signs and symptoms, laboratory measures of safety, Unsolicited AEs, SAEs, AEs of special interest (AESI) and rates of discontinuation

*Primary objectives 2:*

- To determine whether multiple infusions of VRC07-523LS reach and maintain detectable levels in the mucosa
- To correlate levels of VRC07-523LS in serum and the mucosa

*Primary endpoints 2:*

- Levels of VRC07-523LS in genital and rectal secretions, as well as cervical, vaginal, and rectal tissues at the collection timepoints
- Levels of VRC07-523LS in serum out to Week 48, 16 weeks after the last product administration

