## 6 Statistical considerations

### 6.1 Accrual and sample size calculations

Recruitment will target accruing a total of 24 healthy, HIV-1–uninfected adult participants in two treatment groups, with 12 participants assigned to each group.

In Group 1, all study participants will receive three IV administrations of VRC07-523LS at the 10 mg/kg dose level. In Group 2, all study participants will receive three IV administrations of VRC07-523LS at the 30 mg/kg dose level.

In both groups, the three infusions will be administered every 16 weeks.

Participants will be randomly assigned to either one of the groups. Groups 1 and 2 will open to randomization at the same time.

In Groups 1 and 2, every study participant will be followed for 12 months (including 8 months of product administration plus 4 months of follow-up) from the day of first product administration.

To ensure balance in the trial of both sexes assigned at birth, the trial will enroll at least and approximately 50% of participants assigned female sex at birth. Randomization will be stratified by assigned sex at birth to ensure balance within each treatment group.

The times at which samples will be collected are listed in [Table 9-1](#) and [Table 9-2](#) for each mucosal site and the blood.

Since enrollment is concurrent with the first biopsy sample collection, all participants will provide some data regarding tolerability of mucosal sample collections. For analyses of VRC07-523LS levels in serum and mucosa and of data from ADA assays, it is possible that data may be missing for various reasons, such as participants terminating from the study early, problems in shipping specimens, or high assay background. Immunogenicity data from 17 phase 1 and 2 phase 2a HVTN vaccine trials, which began enrolling after June 2005 (data as of September 2014), indicate that 17% is a reasonable estimate for the rate of missing data. In HVTN 104 (phase 1 trial of VRC01), approximately 10-15% of drug concentration data were missing at the primary timepoints.

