4 COHORT DEFINITION

Participants will enroll in the study at the first biopsy collection. Only participants who remain in the trial after completion of the first biopsy visit will be randomized. Since enrollment is concurrent with the first biopsy sample collection, all enrolled participants will provide some data regarding the tolerability of mucosal sample collections, regardless of if they are randomized.

Since randomization followed with receiving the first study product administration, all randomized participants will provide some data regarding the safety of the study product. Participants who are randomized but do not receive the study product are released from randomization, so the randomized cohort will consist only of participants who received study product and contribute some data regarding the safety of the study product.

All safety data from randomized participants will be analyzed according to the initial randomization assignment regardless of how many infusions they received. The analysis is a modified intent-to-treat analysis in that individuals who are enrolled but not randomized do not contribute immunogenicity data about the study product and hence are excluded.

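### The one specified solicited-AE table pools all three infusions, so it cannot show whether reactions rise, fall or stay level with repeat dosing

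*Protocol*

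**What the plan says.** Both groups are planned to receive three infusions: "In both groups, the three infusions will be administered every 16 weeks" (Protocol section 6.1).

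For solicited AEs, Protocol section 6.4.3.1 says that numbers and percentages "will be tabulated by severity and treatment arm and the percentages displayed graphically by arm". Within each sign or symptom, a participant's "solicited AEs will be counted once under the maximum severity for all administration visits". Infusion number is not a dimension of the table or the graph.

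On who is included, Protocol section 6.4.3 says "All participants who received at least 1 partial or complete administration of VRC07-523LS will provide some safety data". SAP section 4 adds that safety data are "analyzed according to the initial randomization assignment regardless of how many infusions they received". Neither document defines a denominator by infusions received.

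Four other statements bear on the point:

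- Protocol section 6.4 and SAP section 7 both commit to further analyses that take account of the infusions and doses actually received. Neither names an endpoint, display or denominator.
- Protocol section 9.10 and Appendix F have solicited AEs assessed after each infusion.
- Laboratory abnormalities are tabulated at each post-administration timepoint (Protocol section 6.4.3.3). SAE and AESI listings give the number of administrations received (section 6.4.3.2).
- SAP section 1 describes a pharmacokinetics plan that will be revised before the final safety analysis.

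**The concern.** The primary safety objectives concern a repeated regimen, for example "To evaluate the safety and tolerability of VRC07-523LS administered at 30 mg/kg IV infusion every 4 months". A reader of the results will want to know whether a second or third infusion is tolerated as well as the first. The pooled maximum removes that information from the type of event most closely tied to an individual infusion. Laboratory values and SAEs keep a link to the administration; solicited reactions do not.

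The pooled table also places participants with one infusion and participants with three in the same denominator. Protocol sections 7.3.2 and 7.3.3 allow infusions to be missed or permanently stopped, so exposure within an arm can differ.

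**Working it through.** **The plan's own safety figure.** Protocol section 6.1.1 states at least a 90% chance of one or more events in 12 participants if the true rate is 17.5%. Check: 1 − (1 − 0.175)^12 = 0.9006, which reproduces. No stated figure depends on the solicited-AE counting rule, so the steps below use assumed rates.

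**Step 1: pooling, by counts alone.** Take 12 participants who all receive three infusions, of whom 3 ever have a given reaction. The pooled cell is 3/12 = 25% in every row.

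| Pattern | Infusion 1 | Infusion 2 | Infusion 3 | Pooled |
|---|---|---|---|---|
| First infusion only | 3/12 | 0/12 | 0/12 | 3/12 |
| One new participant each time | 1/12 | 1/12 | 1/12 | 3/12 |
| Third infusion only | 0/12 | 0/12 | 3/12 | 3/12 |
| Same three participants each time | 3/12 | 3/12 | 3/12 | 3/12 |

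The last row has 9 reactions and the others have 3.

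**Step 2: pooling, by expected rates.** Assume independence between infusions within a participant. Then P(any reaction) = 1 − (1 − p1)(1 − p2)(1 − p3).

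- Rising, 5%, 10%, 20%: 1 − 0.95 × 0.90 × 0.80 = 0.316.
- Falling, 20%, 10%, 5%: 1 − 0.80 × 0.90 × 0.95 = 0.316.

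**Step 3: early stopping.** No dosing dropout rate is given. The nearest figure, 17%, is for missing assay data (Protocol section 6.1). Assume a constant 10% risk per infusion, with stopping after infusion 1 unrelated to any reaction.

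- All receive three: 1 − 0.9^3 = 0.271.
- 2 of 12 stop: (10 × 0.271 + 2 × 0.10)/12 = 0.2425, a loss of about 0.3 of a participant in 12.
- 4 of 12 stop: (8 × 0.271 + 4 × 0.10)/12 = 0.214, a loss of about 0.7 of a participant in 12.

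Now start from a true 25% under full dosing and let 1, 2 or 4 of 12 stop after infusion 1:

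| Pattern (per-infusion risk) | 1 stops | 2 stop | 4 stop |
|---|---|---|---|
| First infusion only (25/0/0%) | 25.0% | 25.0% | 25.0% |
| Flat (9.1% each) | 23.7% | 22.4% | 19.7% |
| Growing (3/8/16%) | 23.2% | 21.3% | 17.7% |
| Third infusion only (0/0/25%) | 22.9% | 20.8% | 16.7% |

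Dilution therefore runs from nothing to about 8 percentage points under these assumptions.

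**Step 4: what a by-infusion table could show.** The score intervals in Protocol Table 6-2 are 0 to 24.2% for 0/12, 1.5 to 35.4% for 1/12 and 4.7 to 44.8% for 2/12. By the same method, 3/12 gives 8.9 to 53.2%. These overlap heavily, so the table would describe a pattern without establishing it.

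**The case against.** The strongest objection is that an analysis by actual infusions is already promised, in firm terms, in both documents, and that the SAP in hand is a pharmacokinetics plan whose safety update is still to come. On that view a missing table layout is pending detail. This has force: the pooled table is the only one *specified*, not the only one planned. But the promise would be met by regrouping participants by doses received and re-running the same maximum-severity table, which would still hide the pattern.

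Three stronger readings are tempting and should not be drawn.

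- *That the trial cannot tell a first-dose reaction from one that grows with repeat dosing.* The data are recorded per infusion, so only the specified table is limited. SAE and AESI listings by number of infusions, laboratory tabulations by timepoint, weekly safety team review and monitoring board review about every 4 months (Protocol sections 6.4.3.2, 6.4.3.3, 11.4.2 and 11.1.2) also follow repeat-dose harm.
- *That the protocol predicts two opposite time patterns for this product.* The sentence "Cases of cytokine release syndrome occur most often in the first few hours after the first mAb dose" (Protocol section 4.8) concerns antibodies against lymphocyte surface targets. The same section separates this product from them because its target is viral. The phrase "the consequences of any antidrug responses, if they were to develop" (section 4.2.1) is part of the rationale for repeat dosing and does not forecast rising solicited reactions. It does show that learning about repeat exposure is a purpose of the trial.
- *That an arm with more discontinuation will look better tolerated.* Discontinuation is part of primary endpoint 1 and is tabulated by reason and arm (section 6.4.3.4), so an excess would be visible. Participants stopped because of a solicited reaction are already counted.

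It is also fair to say that 12 per arm gives little precision for each infusion. That argues against a formal test, not against showing the counts.

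**Conclusion.** The point holds for the specified table. The counting rule gives one cell for first-infusion, flat, rising and recurrent patterns, and Step 1 needs no assumed risk to show it. The 31.6% example in Step 2 rests on assumed risks and independence.

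Dilution is a minor, conditional addition. It requires that participants stop before reacting, and it is absent for a first-infusion reaction. Its size depends on stopping rates that the documents do not give; 4 of 12, or 33%, is about twice the 17% missing-assay figure.

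This is an inexpensive gap to close in a descriptive safety analysis. It does not invalidate the safety evaluation.

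**What to change.** Keep the maximum-severity table. In the safety update of the SAP, add:

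1. A tabulation of each solicited sign or symptom by infusion number (1, 2, 3) and arm. Count participants at the maximum severity reached after that infusion, with those who received that infusion as the denominator, and give score intervals.
2. The same tabulation restricted to participants who received all three infusions, so that a change over infusions can be read in a fixed set of people.

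State that these tables are part of what the promised analyses by actual infusions mean for solicited AEs, and that they are descriptive with no formal test.

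The cost is a little programming, since the data are already collected at each infusion. The drawbacks are wide intervals at 12 or fewer per cell, and selection in the infusion 2 and 3 denominators, which include only participants still being dosed. The second tabulation fixes the set of people but is itself selected. No dosing or stopping rule changes.

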#### **6.4.3.2 SAEs and Unsolicited AEs**

Unsolicited AEs will be summarized using MedDRA System Organ Class and preferred terms. Tables will show by treatment arm the number and percentage of participants experiencing an Unsolicited AE within a System Organ Class or within preferred term category by severity or by relationship to study product. For the calculations in these tables, a participant with multiple Unsolicited AEs within a category will be counted once under the maximum severity or the strongest

recorded causal relationship to study product. Formal statistical testing comparing arms is not planned since interpretation of differences must rely heavily upon clinical judgment.

A listing of SAEs reported to the DAIDS Regulatory Support Center (RSC) Safety Office will provide details of the events including severity, relationship to study product, time between onset and last study product administration, and number of study product administrations received. A separate listing will do the same for AESI. A list of AESI to be reported for this protocol is provided in [Appendix H](#).

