Most infusion-related events occur within the first 24 hours after beginning administration. Delayed allergic reactions to a mAb may include a serum sickness type of reaction, characterized by urticaria, fever, lymph node enlargement, and joint pains. These symptoms may not appear until several days after the exposure to the mAb and are noted to be more common with chimeric types of mAb (51).

Reactions related to the rate of infusion have been described for several FDA-licensed mAbs. With licensed therapeutic mAbs, cytokine-mediated infusion reactions, including cytokine release syndrome, are typically managed by temporarily stopping the infusion, administering histamine blockers and restarting the infusion at a slower rate (53). Supportive treatment may also be indicated for some signs and symptoms.

To date, the clinical trial safety experience with VRC01-class mAbs has been reassuring:

- In HVTN 104, IV administration of VRC01 was generally well-tolerated with mild pain and/or tenderness commonly reported at the site of the IV infusion. Mild to moderate systemic reactogenicity symptoms were reported by VRC01 recipients following at least one of the infusions, but there was no clear relationship with frequency or severity to the dose of VRC01 (48).
- No hypersensitivity reactions or cytokine release syndrome symptoms were reported in HVTN 104 (48).
- The ongoing blinded HVTN 704/HPTN 085 and HVTN 703/HPTN 081 trials have reported an approximately 1% rate of urticaria or similar reactions.
- In the ongoing VRC 605 trial of VRC07-523LS, there have been no SAEs and no safety pauses. The maximum severity of related AEs has been Grade 1 (for 17 events) and Grade 2 (for 6 events, including 2 infusion reactions).
- Serious reactions associated with mAb administration, such as acute anaphylaxis, serum sickness, ADAs, and increased risk of infections have not been observed to date in trials of VRC01-class mAbs.

There is a possibility that receipt of the study product will cause a reactive result on some currently available HIV test kits, especially if testing occurs close to study product administration timepoints (see Section 9.7.1).

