### **5.3 Exploratory objectives**

*Exploratory objective 1:*

To assess the acceptability and tolerability of repeat mucosal sampling, including secretions and biopsies, for application in future studies

*Exploratory objective 2:*

To develop predictive mucosal population pharmacokinetic models of VRC07-523LS administered IV

*Exploratory objective 3:*

To conduct analyses related to furthering the understanding of HIV, monoclonal antibodies, immunology, vaccines, and clinical trial conduct

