#### **11.2.2 AE reporting**

An AE is any untoward medical occurrence in a clinical investigation participant administered a study product/procedure(s) and which does not necessarily have a causal relationship with this treatment. An AE can therefore be any unfavorable and unintended sign (including an abnormal laboratory finding), symptom, or disease temporally associated with the use of an investigational study product/procedure(s), whether or not related to the investigational study

product/procedure(s). See the Ab MOP and SSP for further detail regarding Solicited and Unsolicited AEs.

The study Unsolicited AE reporting period is from study enrollment of a trial participant to completion of the safety contact two weeks after the last biopsy collection at Week 50.

All AEs are graded according to the Division of AIDS (DAIDS) Table for Grading the Severity of Adult and Pediatric Adverse Events, Corrected Version 2.1, July 2017, available on the RSC website at <http://rsc.tech-res.com/clinical-research-sites/safety-reporting/daids-grading-tables>, except:

- Unintentional Weight Loss is required to be reported as an AE only if it is considered to be potentially deleterious to the participant's health (see HVTN 128 SSP);
- Infusion Site Erythema or Redness and Infusion Site Induration or Swelling will not consider interference with usual social and functional activities such that:
  - Grade 1 is: 2.5 to < 5 cm in diameter OR 6.25 to < 25 cm^2 surface area;
  - Grade 2 is: ≥ 5 to < 10 cm in diameter OR ≥ 25 to < 100 cm^2 surface area;
  - Grade 3 is: ≥ 10 cm in diameter OR ≥ 100 cm^2 surface area OR Ulceration OR Secondary infection OR Phlebitis OR Sterile abscess OR Drainage;
  - Grade 4 is: Potentially life-threatening consequences (eg, abscess, exfoliative dermatitis, necrosis involving dermis or deeper tissue);
- Monoclonal antibody reactions (see HVTN 128 SSP)

All AEs are reported to the SDMC on the appropriate CRF. Clinic staff should evaluate every AE to determine if (1) the AE meets the requirements for expedited reporting to DAIDS (see Section 11.2.3) and (2), and (3) if the AE is listed as an AESI. A list of AESI to be reported in this protocol is provided in [Appendix H](#).

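### The Unsolicited AE tables show severity and product relationship separately, so in general they cannot give the severity of product-related non-serious events

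*Protocol*

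**What the plan says.** Protocol Section 6.4.3.2 plans tables by arm that count, with percentages, those "experiencing an Unsolicited AE within a System Organ Class or within preferred term category by severity or by relationship to study product". Under its counting rule "a participant with multiple Unsolicited AEs within a category will be counted once under the maximum severity or the strongest" relationship on record. No formal test between arms is planned.

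The same section adds a listing of SAEs reported to the DAIDS safety office, which will "provide details of the events including severity, relationship to study product, time between onset and last study product administration" and the number of administrations received. For adverse events of special interest, "A separate listing will do the same for AESI". Those events are the autoimmune and related conditions in Appendix H. Section 6.4.3.3 sends reportable laboratory abnormalities without a clinical diagnosis into the same AE tables.

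On procedures, Section 11.2.2 defines an AE as something "temporally associated with the use of an investigational study product/procedure(s), whether or not related to the investigational study" product or procedure. Exploratory objective 1 (Section 5.3) is "To assess the acceptability and tolerability of repeat mucosal sampling, including secretions and biopsies, for application in future studies". Protocol Section 6.1 and SAP Section 4 both say that everyone enrolled informs the tolerability of sampling. SAP Section 4 says this applies whether or not they are randomized.

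The SAP contains pharmacokinetic and anti-drug-antibody outputs but no safety tables. Its Section 1 says it will be revised before the final safety analysis.

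**The concern.** Primary objective 1 is the safety and tolerability of the product at each dose. All participants receive product, so no control arm shows the background rate of events. The investigator's attribution is then one of the main means of separating product events from biopsy events and intercurrent illness. The natural summary is the worst grade among events judged related, by arm.

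The protocol relies on that quantity elsewhere. Section 7.3.3 stops a participant's product according to grade combined with relatedness. Table 11-1 triggers a pause, or a review to consider one, on the same combination. Section 4.8 describes the earlier VRC07-523LS trial in those terms: "The maximum severity of related AEs has been Grade 1 (for 17 events) and Grade 2 (for 6 events, including 2 infusion reactions". It also reports that HVTN 127/HPTN 087 has had no related AE of Grade 3 or higher. If the final tables cannot produce this summary, the trial's safety result cannot be set beside the evidence that the protocol cites.

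**Working it through.** No stated figure is in dispute. The check is of the table specification, followed by a bound on what the two tables together can reveal.

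**1. Is this one table or two?** The layout in 6.4.3.2 offers severity or relationship, and the counting rule names a separate maximum for each. These are two one-way reductions. Neither document specifies a severity-by-relationship table.

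**2. What is lost?** Take a participant with an unrelated Grade 3 event and a related Grade 1 event in the same System Organ Class. The severity table counts the participant at Grade 3, and the relationship table counts the same participant as related. A participant with one related Grade 3 event gives identical entries.

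**3. How wide is the ambiguity?** For one category in one arm, let
- S = participants whose maximum severity is Grade 3, with none higher;
- R = participants whose strongest relationship is related;
- J = participants with at least one event that is both related and Grade 3.

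Then 0 ≤ J ≤ min(S, R). The lower bound stays at 0 even when S and R are the same people, because participants can have several events.

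The values of S and R below are assumptions; n = 12 per arm is from Section 6.1.

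| S, R | Possible J | J/12 | 95% score interval, lowest J | 95% score interval, highest J |
|---|---|---|---|---|
| 1, 1 | 0 to 1 | 0% to 8.3% | 0 to 24.2% | 1.5 to 35.4% |
| 2, 2 | 0 to 2 | 0% to 16.7% | 0 to 24.2% | 4.7 to 44.8% |
| 3, 3 | 0 to 3 | 0% to 25% | 0 to 24.2% | 8.9 to 53.2% |

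The intervals for 0/12, 1/12 and 2/12 are those in protocol Table 6-2, and recomputing them reproduces them to within rounding. The interval for 3/12 was computed by the same score method. If S or R is zero, J is zero and nothing is lost.

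**4. Do other planned outputs recover the cross?**
- *SAE and AESI listings:* yes, event by event, but only for those events.
- *Discontinuation table (6.4.3.4):* partly. Section 7.3.3 stops product for most related Grade 3 clinical events and for confirmed related Grade 3 or 4 laboratory abnormalities, so some will show as reasons. It exempts fever and subjective symptoms. Events after the third infusion at Week 32 leave no product to discontinue.
- *Safety team review (Table 11-1):* related Grade 3 and 4 AEs are reviewed, apart from listed subjective solicited symptoms. This is monitoring, not a final-analysis output.
- *Grades 1 and 2:* for non-serious, non-AESI events neither route generally applies. Yet this is where the earlier trial's related events fell: 17 at Grade 1 and 6 at Grade 2, so 6/(17 + 6) = 26% at Grade 2. The planned tables could not in general produce the matching split here.

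**5. Sampling tolerability.** Enrollment is the baseline biopsy visit on day −14, before randomization (Section 9.3). AE reporting starts at enrollment (Section 11.2.2). Section 6.4.3 bases safety data on participants given product, and the AE tables are by treatment arm. A person biopsied at baseline and not randomized has no arm, so an AE in that person has no place in the planned AE tables. Section 6.4.3.5 tabulates acceptability of product administration and infusion only. Appendix F schedules a mucosal sampling acceptability questionnaire, but neither document specifies an analysis of it.

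**The case against.** The strongest reply is that the table set is not final. Section 6.4.3.2 is a summary, Section 6.4.4.1 leaves further analysis detail to the SAP, and the SAP promises a revision before the final safety analysis. An extra crossed table is a routine decision at the table-shell stage. This stands, and it sets the size of the point: nothing has gone irreversibly wrong and the fix has an obvious home.

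A reader might infer that non-serious related Grade 3 events appear nowhere. They do appear. They are counted in both tables, some surface as reasons for discontinuation, and Table 11-1 sends most of them to prompt review. They simply cannot be identified as related Grade 3 in the tables.

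A reader might also infer that biopsies outnumber infusions and so swamp the product signal. There are 24 × 4 = 96 scheduled biopsy visits and 24 × 3 = 72 infusions. But 24 of those biopsy visits precede any product, which leaves 72 against 72. The later biopsies fall 14, 14 and 112 days after an infusion (Table 9-1). Solicited reactions are captured on the infusion day and the three days after and are tabulated separately by severity. Timing therefore helps to separate acute infusion reactions from biopsy complications.

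Nor do the documents show that procedure causality goes uncollected. The AE form, the antibody manual of operations and the study-specific procedures are not in the file. Section 4.8 reports procedure-related events from HVTN 116, so they were identified in that trial. The complication counts in Section 4.8 do not support an expected number for this trial: the reports are of mixed kinds, are not all described as procedure-related, and come from trials with different biopsy numbers.

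**Conclusion.** The gap holds for Unsolicited AEs that are neither serious nor of special interest. As specified, the tables cannot in general give the severity of product-related events. With assumed counts of 2 and 2 in an arm of 12, the related Grade 3 rate is fixed only to between 0% and 16.7%. The finding itself rests on the table layout and the counting rule, not on those counts.

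It is a reporting gap, not an error in data collection or monitoring, and it invalidates no figure in the plan. It is worth closing because the missing summary is the one the protocol acts on and cites, there is no placebo arm, and the fields are already recorded.

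The sampling part is weaker. It concerns an exploratory objective, and biopsy-type terms will still appear in the tables, without attribution. What stands is that no planned AE output is organised around biopsies, and that participants enrolled but not randomized fall outside the arm-based tables although both documents count them for tolerability.

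**What to change.** **Main change.** At the SAP revision before the final safety analysis, add to the Section 6.4.3.2 outputs a table by arm of participants with product-related Unsolicited AEs, by System Organ Class and preferred term, at maximum severity. Take the maximum over related events only. The cost is one extra table, which will be sparse with 12 per arm. It needs no new data.

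**Secondary suggestion.** Add a short event-level listing of AEs with onset after a biopsy visit. Show days since the last biopsy, severity and, only if already collected, relationship to the procedure. Include participants who were enrolled and biopsied but not randomized. Since enrollment is itself a biopsy visit, an onset window is needed to keep the listing short. Fourteen days would match the interval that the protocol uses between the last biopsy visit and the safety contact (day 350 − day 336 = 14). The cost is one listing from existing fields.

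A new causality item on the AE form is not proposed. SAP Section 8.3 already reports on post-baseline serum concentrations, so post-dose data exist and attribution would probably have to be made retrospectively. A table by specimen type and visit would be too sparse to be useful.
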